11.6.2.3 Questionnaires

11.6.2.3.1 Urge-to-Smoke Questionnaire of Smoking Urges Brief

The total score and the two factors from the QSU-brief will be listed for all scheduled time points and summarized overall and by the two stratification factors (sex, CC nicotine level at Admission) for the PK populations, as specified in Section 11.1.1 "Stratified Presentation". The individual responses to all questions will be listed by product, study day, and assessment time points.

In addition line graphs will be produced for the total score and factors means (and 95% CI) over all timepoints.

Philip Morris Products S.A. Protocol ZRHR-PK-01-EU

Statistical Analysis Plan Final v 3.0 / 08 May 2014 Confidential Page 51 of 72

The analysis of the subjective effects of smoking (the total score, and Factor-1 and Factor-2 from the QSU-brief) will be performed using the same mixed effects ANOVA adopted for the analysis of CO breath test described in Section 11.6.2.2.1 "Exhaled CO and COHb".

A sensitivity analysis using bootstrap techniques, will also be conducted on the total and factors score of QSU-brief, as described in Section 11.6.3 "Supportive/Sensitivity Analysis".

The main comparison will be the mean difference over all timepoints. LS means for each product, the overall mean difference (THS 2.2 - CC or THS 2.2 - NNS as appropriate) and the mean differences at each time point will be presented in the tables as a point and interval (95% CI) estimate. Figures of the LS mean difference and 95% CI at each time point will be produced.

The data will be presented in the below outputs:

TFL number	Title
TABLES	
15.2.4.12	Analysis of QSU-brief Questionnaire Factors and Total Score – PK
	Population
15.2.4.14	Descriptive Statistics of QSU-brief Questionnaire Factors and Total
	Score – PK Population
15.2.4.14.1	Descriptive Statistics of QSU-brief Questionnaire Factors and Total
	Score by Sex – PK Population
15.2.4.14.2	Descriptive Statistics of QSU-brief Questionnaire Factors and Total
	Score by Nicotine Level – PK Population
FIGURES	
15.1.2.10.1	QSU-brief Factors and Total Score Profiles Arithmetic Mean (± 95% CI)
	– Group-1 PK Population
15.1.2.10.2	QSU-brief Factors and Total Score Profiles Arithmetic Mean (± 95% CI)
	– Group-2 PK Population
15.1.2.11.1	QSU-brief Factors and Total Score Profiles Arithmetic Least Squares
	Mean Differences (± 95% CI) – Group-1 PK Population
15.1.2.11.2	QSU-brief Factors and Total Score Profiles Arithmetic Least Squares
	Mean Differences (± 95% CI) – Group-2 PK Population
LISTINGS	
15.3.6.11	Listing of QSU-brief Questionnaire Results

11.6.2.3.2 Modified Cigarette Evaluation Questionnaire

The MCEQ domain scores composed of the three multi-item subscales and two single items from the MCEQ will be listed and summarized overall and by the two stratification factors (sex, CC nicotine level at Admission) for the PK populations, as specified in Section 11.1.1 "Stratified Presentation". The individual responses to all questions will be listed.

Philip Morris Products S.A. Protocol ZRHR-PK-01-EU Statistical Analysis Plan Final v 3.0 / 08 May 2014 Confidential Page 52 of 72

A mixed effects ANOVA model will be used to estimate mean THS 2.2-CC differences of the MCEQ domain scores and variances, with a REML method, using heterogeneous compound symmetry covariance structure (**Brown and Prescott**, 1999). Subjects within sequence will be used as random effects and fixed effects are period, sequence, and product exposure.

```
Proc mixed data=_data__method=reml maxiter=200;
Class subject sequence product period;
Model response = sequence period product;
Random subject(sequence) / subject=subject type=csh;
Lsmean product / pdiff =control('CC') alpha=0.05 cl;
Run;
```

In case of model convergence issues, additional covariance structures will be investigated with the following order: heterogeneous autoregressive(type=arh), variance component (type=vc), and unstructured (type=un).

LS means for each product and the overall point and 95% interval estimate of the difference (THS 2.2 - CC) will be presented in the tables.

A sensitivity analysis using bootstrap techniques, will also be conducted on the MCEQ domain scores, as described in Section 11.6.3 "Supportive/Sensitivity Analysis".

The data will be presented in the below outputs:

TFL number	Title
TABLES	
15.2.4.15	Analysis of MCEQ Subscales – PK Population
15.2.4.17	Descriptive Statistics of MCEQ Subscales – PK Population
15.2.4.17.1	Descriptive Statistics of MCEQ Subscales by Sex – PK Population
15.2.4.17.2	Descriptive Statistics of MCEQ Subscales by Nicotine Level – PK
	Population
LISTINGS	-
15.3.6.12	Listing of MCEQ Questionnaire Results

11.6.3 Supportive/Sensitivity Analysis

To support the interpretation of the PK analysis, the values of nicotine concentration greater than BLOQ before T_0 will be listed together with any PK parameters excluded from the analysis. Listing will be presented by PK parameter impact, sequence, period and study date.

To better understand the impact of the higher than expected T_0 values, an analysis of the PK parameters will be performed as described above, however the data for subjects with their T_0 values >5% of their C_{max} value will be excluded from the analysis.

Philip Morris Products S.A. Protocol ZRHR-PK-01-EU Statistical Analysis Plan Final v 3.0 / 08 May 2014 Confidential Page 53 of 72

Sensitivity analysis will be conducted on the C_{max} and $AUC_{(0-last)}$ endpoints for the Group-1 and Group-2 PK populations should there be 20% or more missing PK parameter values. This analysis is conducted on all the available PK parameters and subjects will be excluded from the analysis if the nicotine concentration T₀ value is >5% of their C_{max} value. The analysis will be conducted in the natural log scale using the same mixed effects ANOVA model described in Section 11.6.2.3.2 "Modified Cigarette Evaluation Questionnaire". Point and 95% interval estimates of the ratios will be back-transformed by exponentiation and tabulated.

The same sensitivity analysis for C_{max} and $AUC_{(0-last)}$ endpoints will be conducted on t_{max} , in both Group-1 and Group-2 PK populations, supporting with THS 2.2 effect estimates on t_{max} adjusted for period, sequence, and subject within sequence.

In case any time information is imputed for the computation of PK parameters as described in Section 11.1.5 "Handling of Dropouts or Missing Data (including outside the limits of quantification)" in any PK population, the median t_{max} for THS 2.2 will be calculated following the imputation of missing time data by 0 sec and 30 sec. If the difference between the two median t_{max} is larger than 5%, a supportive analysis will be conducted by repeating the analyses described in Section 11.6.1 "Primary Analyses" and 11.6.2 "Secondary Analyses" on the t_{max} , AUC_(0-last), and AUC_(0-t') endpoints estimated by means of the imputation of missing time by 0 sec.

To evaluate the sensitivity to the distributional assumptions for the QSU-brief (see Section 11.6.2.3.1 "Urge-to-Smoke Questionnaire of Smoking Urges Brief") and MCEQ (see Section 11.6.2.3.2 "Modified Cigarette Evaluation Questionnaire") questionnaire scores, point and 95% interval estimates will also be assessed by means of the percentile bootstrap technique, using 2000 bootstrap samples which preserve the number of subjects per sequence.

The data will be presented in the below outputs:

TFL number	Title
TABLES	
15.2.4.3	Analysis of Pharmacokinetic Parameters of Nicotine by Bootstrapping
	Techniques
15.2.4.4	Analysis of Pharmacokinetic Parameters of Nicotine by Zero Sec
	Imputation – PK Population
15.2.4.13	Analysis of QSU-brief Questionnaire Factors and Total Score by
	Bootstrapping Techniques – PK Population
15.2.4.16	Analysis of MCEQ Subscales by Bootstrapping Techniques – PK
	Population

11.6.4 Safety Evaluation

Safety variables monitored in this study include: AEs; vital signs (systolic and diastolic blood pressure, pulse rate, respiratory rate); spirometry; ECG data; concomitant

Philip Morris Products S.A. Protocol ZRHR-PK-01-EU Statistical Analysis Plan Final v 3.0 / 08 May 2014 Confidential Page 54 of 72

medication, clinical chemistry, hematology, urine analysis safety panel, BMI, physical examination, respiratory symptoms (cough assessment).

The primary analysis of Safety parameters will be conducted on the Safety population as described in Section 11.1.3 "Descriptive Statistics".

11.6.4.1 Safety Reporting

An exposure emergent AE is defined as an AE that occurs after first product use or that is present prior to first product use and becomes more severe after first product use. All other AEs will not be summarized but provided in listings only.

All AEs occurring from the signing of informed consent will be recorded electronically. The AE listings will include all AEs captured in the database at any time during the study (including those from subjects who were not in the safety population). All AEs occurred after the product test of THS 2.2 or NNS will be included in the summary tables. During the screening period prior to the first THS 2.2 or NNS product use, only study procedure related AEs will be included in the summary tables.

AEs reported from subjects that have a first product use, but were not randomized will be summarized in a separate sequence: "Exposed but not randomized". The remainder of safety endpoints assessed in enrolled subjects that have a first product use, but were not randomized will be summarized in a separate sequence: "Enrolled but not randomized".

Partial dates will not be imputed, but assumptions will be made as follows to assign to exposure-emergent or not:

Date information	Assign as
Partial date, e.gMay2012, or2011. If month/year	Exposure-
is the same as, or later than the month and/or year of	emergent
Screening.	
Partial date, e.gMay2012, or2011. If month	Not exposure-
and/or year is earlier than the month and/or year of	emergent
Screening.	

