6 INVESTIGATIONAL PLAN

6.1 Study Design

This is a randomized, controlled, 2-period, 4-sequence, single use crossover study. An incomplete block design has been adopted, where each subject will receive two of the three products (Figure 1):

- THS 2.2.
- CC.

Philip Morris Products S.A. Protocol ZRHR-PK-01-EU

Statistical Analysis Plan Final v 3.0 / 08 May 2014 Confidential Page 14 of 72

• NNS.

In total, 62 eligible, healthy smoking subjects will be randomized into one of the 4 sequences in Table 1:

Table 1 Definition	of Randomization	Groups and Sequences
		eroups and bequences

Group	Allocation Ratio	Sequence	Sample Size
•	0.0	1. THS 2.2 then CC	22
Group-1 = THS 2.2 vs. CC	2:2	2. CC then THS 2.2	22
	4.4	3. THS 2.2 then NNS	9
Group-2 = THS 2.2 vs. NNS	1:1	4. NNS then THS 2.2	9

A Screening Visit will be conducted within 4 weeks prior to Admission to the investigational site (Day -29 to Day -2). A demonstration of the THS 2.2 product and the NNS will also be done by the site staff during the screening visit. Subjects will be admitted to the clinic on Day -1 (Admission). On Day -1, as the last procedure of the eligibility assessments on that day, all subjects will undergo a product test prior to enrolment, first THS 2.2 (using up to three Tobacco Sticks) and subsequently the NNS (1 spray of 0.5 mg per nostril as per label). In female subjects, the urine pregnancy test must be negative before the product test is performed with either THS 2.2 or NNS. After all inclusion and exclusion criteria have been satisfactorily met, only subjects willing and ready to use both the THS 2.2 and NNS products can be enrolled. Screening procedures do not necessarily have to be conducted on the same day.

Subjects are enrolled on Day -1, but not randomized until the Day 0 washout, therefore it is possible to have enrolled subjects who do not get randomized.

[figure not shown]
Subjects will be discharged from the investigational site in the morning of Day 4 after all safety examinations of the Day of Discharge have been conducted. After Discharge, subjects will enter into a 7-day safety follow-up to capture spontaneously reported new AEs/SAEs and for active follow-up of ongoing AEs/SAEs. Any AE will in general be followed up until resolved, stabilized i.e., no worsening of the event, or until a plausible explanation for the event has been found.

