11.6.4.5 Vital Signs, Physical Findings and Other Observations Related to Safety

11.6.4.5.1 Prior and Concomitant Medication

Prior medication is defined as any medication that started and ended prior to Screening. Concomitant medication is defined as any medication starting on or after Screening. Medications that started prior to Screening and are ongoing at Screening are considered as concomitant.

All medications will be listed by sequence using PT and Anatomical Therapeutic and Chemical (ATC) codes (World Health Organization - Drug Dictionary Enhanced [WHO-DDE] Q1 2013). A flag will be presented on the listing indicating whether the medication is prior or concomitant. Partial dates will not be imputed, but assumptions will be made as follows to assign to either prior or concomitant:

Date information	Assign as
Missing stop date	Concomitant
Partial date, e.gMay2012, or2011. If month/year	Concomitant
is the same as, or later than the month and/or year of	
Screening.	
Partial date, e.gMay2012, or2011. If month	Prior
and/or year is earlier than the month and/or year of	
Screening.	

Prior and concomitant medications will be listed by sequence. Concomitant medications will be summarized for the Safety population showing the number (%) of subjects who used the medication at least once by sequence and by ATC 1st and 2nd levels medical term and by preferred drug name. Listings will be provided by sequence and will display original dates (no imputation).

Philip Morris Products S.A. Protocol ZRHR-PK-01-EU Statistical Analysis Plan Final v 3.0 / 08 May 2014 Confidential Page 60 of 72

The data will be presented in the below outputs:

TFL number	Title
TABLES	
15.2.6.8.1	Summary of Prior Medication by Anatomical Therapeutic Classes
15.2.6.8.2	(ATC) 1 and 2 – Safety Population
13.2.0.8.2	Summary of Prior Medication by Preferred Drug Name – Safety Population
15.2.6.9.1	Summary of Concomitant Medication by Anatomical Therapeutic Classes (ATC) 1 and 2 – Safety Population
15.2.6.9.2	Summary of Concomitant Medication by Preferred Drug Name – Safety Population
LISTINGS	~
15.3.6.3	Listing of Prior and Concomitant Medication

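### The partial-date rule for exposure-emergent AEs is anchored to the Screening month, although the same section defines exposure-emergent by first product use

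*SAP*

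**What the plan says.** Section 11.6.4.1 (Safety Reporting) sets the reference point: "An exposure emergent AE is defined as an AE that occurs after first product use", or one already present that becomes more severe after that use. Other AEs are listed but not summarized. The section also says that AEs before the first THS 2.2 or NNS use enter the summary tables only if related to a study procedure.

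First product use is the Admission test. Section 6.1 states: "On Day -1, as the last procedure of the eligibility assessments on that day, all subjects will undergo a product test prior to enrolment". Section 11.6.4.1 names the product test as the point from which all AEs are tabulated, and section 10.2 counts it as exposure.

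The partial-date table in section 11.6.4.1 uses another anchor. It is introduced with "Partial dates will not be imputed, but assumptions will be made as follows to assign to" exposure-emergent or not. An AE is exposure-emergent if its month/year "is the same as, or later than the month and/or year of" Screening. It is not exposure-emergent if its month "and/or year is earlier than the month and/or year of" Screening. Section 6.1 places Screening on Day -29 to Day -2.

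On recording, section 11.6.4.1 says: "All AEs occurring from the signing of informed consent will be recorded electronically". The assessment schedule in section 15.1 puts consent at Screening.

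**The concern.** The definition and the rule that applies it to incomplete dates use different reference points. A partial date can be enough to show that an AE began before the subject touched a study product, and the table still calls it emergent.

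The same two-row date rule appears in section 11.3.5 for medical history and in section 11.6.4.5.1 for medication. Both of those sections define their categories by Screening (for example "Prior medication is defined as any medication that started and ended prior to Screening"), so the anchor fits there. It does not fit a category defined by first product use.

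At stake is the content of the AE summary tables: events that the section itself says are to be listed only could be tabulated as exposure-emergent.

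**Working it through.** The SAP states no figure on this point, so there is none to reproduce. The check sets the rule against the definition and then asks how often the calendar allows them to disagree.

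**Inputs**
- Reference point of the definition: product test, Day -1 (sections 11.6.4.1 and 6.1).
- Reference point of the partial-date rule: month/year of Screening (section 11.6.4.1).
- Gap from Screening to Day -1: from (-1) - (-2) = 1 day to (-1) - (-29) = 28 days (section 6.1).
- Distribution of that gap: not given. A uniform spread over 1 to 28 days is used below as an assumption.

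**Step 1: a case where the rule gives the wrong class.** Screening 20 May, product test 5 June, onset recorded only as May. Every day in May precedes 5 June, so onset is certainly before exposure. May equals the Screening month, so the table assigns exposure-emergent. Unless the AE became more severe after 5 June, this contradicts the definition. If it is also not procedure-related, it enters tables that should exclude it.

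**Step 2: can the second row be reached?** AEs are recorded from consent, and consent is at Screening. An AE arising after consent cannot have an onset month earlier than the Screening month. Section 6.1 allows screening procedures on different days, so exceptions are conceivable, but the not-emergent row is almost never used. The table therefore sends nearly every partially dated AE to emergent.

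**Step 3: how often do Screening and Day -1 straddle a month boundary?** With Admission dates spread evenly over 2013 to 2016 (48 months, 1,461 days, so 1,461/48 = 30.44 days per month), a gap of g days, with g no more than 28, straddles a boundary with probability g/30.44.

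| Gap (days) | Calculation | Probability |
|---|---|---|
| 1 | 1/30.44 | 3% |
| 7 | 7/30.44 | 23% |
| 14 | 14/30.44 | 46% |
| 21 | 21/30.44 | 69% |
| 28 | 28/30.44 | 92% |
| Uniform 1 to 28 (assumed) | 14.5/30.44 | 48% |

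A count over every Admission date in those four years gives the same values.

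**Step 4: how many pre-exposure onset days could be recognised as such?** An onset k days before Day -1 falls in an earlier month with probability k/30.44. Weight every pair of gap g (1 to 28) and onset k (1 to g) equally. The mean of k is then the sum of g(g+1)/2 divided by the sum of g, that is 4,060/406 = 10.
- Day missing, month and year known: 10/30.44 = 33% of pre-exposure onset days are certainly before first use.
- Year only: 10/365.25 = 3%.

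The SAP's rule classes none of these days as not emergent. A rule anchored to first product use would do so for the 33% and the 3%. The rest share a month (or year) with first use, are truly ambiguous, and would stay emergent.

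**The case against.** The strongest defence is that counting an AE as emergent when its timing is unclear is the cautious choice in safety reporting. That stands where the partial date shares its month with first product use. It does not cover dates that already place onset before exposure, because there the timing is not unclear.

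A reader might infer more than the documents support, in three ways:
- **That every AE dated only to an earlier Screening month is misclassified.** An AE present before first use that becomes more severe afterwards is emergent by definition, whatever its onset month. A procedure-related AE from before first use is tabulated in any case.
- **That about half of subjects or AEs are affected.** The 48% is the chance of straddling a month boundary under an assumed uniform gap. It counts neither AEs nor partially dated AEs.
- **That a product comparison is biased.** Section 9 drops safety analysis by product, section 11.6.4.2 summarizes AEs by sequence and overall, and no AE hypothesis is tested. The listings hold every captured AE.

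A further objection is that simply swapping the anchor could under-count: an AE with onset in the Screening month that worsened after use would fall into the not-emergent row. That is correct, so the replacement wording needs an exception for worsening. The table also does not say whether the partial date is onset or stop. The working above takes it as onset.

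**Conclusion.** The partial-date rule is wrong as written, because it contradicts the definition in its own section and nothing elsewhere in the SAP corrects it. The wrong result is confined to AEs that meet all of these conditions: partial onset date; Screening and Day -1 in different calendar months (or years, for year-only dates); onset month or year wholly before first product use; no worsening after use; and no relation to a study procedure.

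The month-straddling probability runs from 3% to 92% over the permitted gap. The effect on any table cannot be stated, because the number of partial dates is not given. It is probably small in a confined study. The error over-counts and does not hide events, and the PK endpoints are untouched. This is a minor correction, worth making because it costs almost nothing.

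**What to change.** In section 11.6.4.1, replace Screening with first product use (product test, Day -1) in both rows of the partial-date table, and state that the rule applies to the AE onset date. The rows would then read:

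- Onset month/year the same as or later than that of first product use: exposure-emergent.
- Onset month/year earlier than that of first product use: not exposure-emergent, unless the AE became more severe after first product use, in which case it is exposure-emergent as already defined.

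Ties still go to emergent, so the cautious default is kept where the date leaves timing open. The tables in sections 11.3.5 and 11.6.4.5.1 stay as they are. The cost is a few words and one changed condition in the AE derivation, with no new data or analysis. The worsening exception must go in with the new anchor; without it the change would trade a small over-count for a possible under-count.

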11.6.4.2 Adverse Events

A general summary table of AEs will be presented by sequence and overall, including:

- The number of events and the number and percentage of subjects reporting at least one AE.
- The number of events and the number and percentage of subjects reporting at least one study product –related AE, broken down by product relatedness (related to THS 2.2 / CC, related to NNS) and expectedness (expected, not expected).
- The number of events and the number and percentage of subjects reporting at least one AE broken down by severity, including a subject once with worst severity.

Philip Morris Products S.A. Protocol ZRHR-PK-01-EU Statistical Analysis Plan Final v 3.0 / 08 May 2014 Confidential Page 55 of 72

- The number of events and the number and percentage of subjects reporting at least one AE leading to any action taken, broken down by action taken related to the product (combining the following items: product use interrupted, product use reduced, product use stopped), treatment given (yes, no), study discontinuation, other action taken.
- The number of events and the number and percentage of subjects reporting at least one AE related to study procedure.

Additional summary tables of AEs will be presented by sequence and overall, with a breakdown of the number of events, as well as the number and percentage of subjects reporting each AE, categorized by SOC and PT coded according to the MedDRA dictionary (version 16.0):

- The number of events and the number and percentage of subjects reporting at least one AE.
- The number of events and the number and percentage of subjects with at least one AE related to product exposure and expectedness for investigational product (IP; THS 2.2 or CC) and reference point product (NNS).
- The number of events and the number and percentage of subjects with at least one AE leading to study discontinuation.
- The number of events and the number and percentage of subjects with at least one AE related to study procedure.
- The number of events and the number and percentage of subjects with at least one AE by severity (mild, moderate, severe)

If a subject has more than one occurrence of the same AE, the subject will be counted only once within a PT for each sequence, with the worst occurrence based on the presentation (e.g., for presentation by severity = most severe, for presentation by relationship = most related). Missing information on the intensity of AE will be counted as severe.

TFL number	Title
TABLES	
15.2.6.1	Summary of Adverse Events – Safety Population
15.2.6.2.1	Summary of Adverse Events by System Organ Class and Preferred Term – Safety Population
15.2.6.2.2	Summary of Adverse Events by System Organ Class – Safety Population
15.2.6.2.3	Summary of Adverse Events by Preferred Term – Safety Population
15.2.6.3	Summary of Adverse Events by System Organ Class, Preferred Term and Relationship to Study Product Exposure for Investigational Product (THS 2.2 or CC) and Reference Point Product (NNS) – Safety Population

Philip Morris Products S.A.Statistical Analysis PlanConfidentialProtocol ZRHR-PK-01-EUFinal v 3.0 / 08 May 2014Page 56 of 72

TFL number	Title
15.2.6.4	Summary of Adverse Events Leading to Study Discontinuation by
	System Organ Class and Preferred Term – Safety Population
15.2.6.5	Summary of Adverse Events by System Organ Class, Preferred Term
	and Severity – Safety Population
15.2.6.6	Summary of Adverse Events Related to Study Procedure by System
	Organ Class and Preferred Term – Safety Population
LISTINGS	
15.3.6.1.1	Listing of Adverse Events

